1.1 Preface

This statistical analysis plan (SAP) is exclusively based on the following information and documents:

Study Protocol	08-MAY-2018 – Version 6.0
----------------	---------------------------

The objective of this document is to detail the statistical methodology to be used for the final statistical analysis of Biotest Study-Nº 984 ("A prospective, open-label, phase I/III study investigating pharmacokinetic properties of BT524 and efficacy and safety of BT524 in the treatment and prophylaxis of bleeding in patients with congenital fibrinogen deficiency").

This SAP covers the part of the statistical analysis to be conducted PPD .

For the evaluation of pharmacokinetics (PK; fibrinogen antigen) and pharmacodynamics (PD; fibrinogen activity), PK/PD parameters will be derived from time-concentration profiles using adapted methodology, non-compartmental analysis, compartment analysis, or population modelling, as appropriate/ required. This part of the statistical analysis, including the analysis for the primary objective of PK-part, will be conducted by Pharmetheus and is described in a separate analysis plan.

1.2 Timing of statistical analyses

The statistical analysis, for which this SAP applies, is the final analysis after all data of this study is collected, cleaned and locked.

2 Modification History

2.1 Changes to the study protocol

The statistical analysis as specified in this SAP is consistent with the statistical analysis as specified in the study protocol (version 6.0).

In the study protocol age groups were defined to describe/define differences in time points of study assessments to be performed for different age groups (see flowchart of study in study protocol section 3). In the SAP age groups were defined differently for data analyses.

Shift tables specified in the study protocol for safety laboratory assessment will be not used.

No changes in the clinical study protocol were considered necessary by the Sponsor to handle clinical protocol deviations possibly related to the COVID-19 pandemic at the end of the study. It was therefore decided in the Blinded Data Review Meeting (BDRM) of June 25, 2020, that any non-conformities in the study conduct caused by the COVID-19 pandemic will be described in a note to file, and any COVID-19 related protocol deviation per patient will be listed in BDRM minutes and presented in study listings where appropriate.

2.2 Changes to previous SAP versions

The first version of the SAP was based on study protocol version 4.0 and signed on 17-Sep-2015.

The amended SAP version 2.0 was intended to reflect the inclusion and treatment of children 0 to <6 years into the ongoing study 984. This extension of the ongoing study 984 was introduced within the study protocol version 5.0 after the positive opinion of the Paediatric Committee on the agreement of the Paediatric Investigation Plan (EMA-001931-PIP01-16) obtained in March 2017.

The amended SAP version 3.0 is intended to precisely describe the responsibilities of the different CROs to the analysis of the study. Definition of analysis sets was refined and PK population added for the descriptive analysis of PK within this SAP. For the age subgroups it was clarified how age of patients and bleeding events is calculated/defined for the respective analysis sets and study parts. Additional clarification for presentation of data was added where needed and the list of table shells in Appendix 15.1 was updated due to changes made.

3 Study Design

The present study is designed as a prospective, uncontrolled, open-label, multicentre, phase I/III study investigating the 14 day single-dose pharmacokinetic and pharmacodynamic properties, efficacy and safety of BT524 following intravenous administration in the treatment or prophylaxis of bleeding in patients with congenital afibrinogenemia or severe congenital hypofibrinogenemia.

The study is divided into two study parts (part I and part II), briefly described in the following:

Table 1: Overview of Study Design and Endpoints

PART I	PART II
	(Individual follow-up 49 ± 4 days after the last administration of BT524)
BT524 Single IV Infusion (70 mg/kg BW)	On-Demand Treatment (ODT) On-Demand Prophylaxis (ODP) BT524 Single or repetitive IV Infusion(s) as individually required
Pharmacokinetics (PK) Pharmacodynamics (PD)	Clinical Efficacy
n = 20 patients ≥ 6 to ≤ 75 years and at least 3 patients 0 to < 6 years In total: n = 23 patients (part I)	All patients who have completed part I (n = 23) and additional patients without PK/PD: at least 10 patients ≥ 6 to ≤ 75 years and at least 3 patients 0 to < 6 years In total (planned): n ≥ 36 patients (part II)
1-2 months	min. 12 months
Surrogate Efficacy	
Safety	

Part I

Part I is focused on the primary endpoint of the study, the 14 day single-dose pharmacokinetics, and on the 14 day single-dose pharmacodynamics and the evaluation of the maximum clot firmness (MCF) as a surrogate efficacy parameter. Moreover, safety will be investigated (by physical examination, vital signs, routine lab parameters, adverse events, development of fibrinogen antibodies and coagulation activation monitoring).

20 patients ≥ 6 to ≤ 75 years and at least 3 patients < 6 years are to be enrolled in part I. With respect to safety, study-specific enrolment procedures comprising consecutive

enrolment of the first five patients with a treatment-free safety interval of 7 days between each patient and restriction in age are implemented (see protocol).

Maximum duration of individual study participation in part I is up to 66 ± 4 days for eligible screened patients (in case the patient does not experience a bleeding event within this safety interval).

Part II

Part I will subsequently be extended to a part II in which individual patients will be investigated for the efficacy and safety of single and/or repetitive administrations of BT524 in on-demand prophylaxis (ODP) and/or on-demand treatment (ODT) of different bleeding events [e.g., (elective) surgical procedure, spontaneous or posttraumatic severe bleeding], if required. Thus, part II is expected to comprise a variety of singular events of different types, severity, and BT524-dosing requirements. All patients who have taken part in the pharmacokinetic assessment (part I) without severe post-dosing complications ideally remain enrolled and will continue treatment for ODP and/or ODT with BT524 in part II.

At least 10 additional patients ≥ 6 to ≤ 75 years and at least 3 additional patients < 6 years will be treated in part II (ODP/ODT) without PK/PD assessments (part I).

Duration of individual study participation is variable and depends on the time point of the last bleeding episode necessitating application of study medication. For the last patient included the minimum duration is 12 months (12 months plus 49 ± 4 days in case the patient experiences a bleeding event at the very end of his/her individual study participation on the last day of month 12).

Efficacy of BT524 will be assessed by clinical endpoints such as the overall hemostatic response to treatment (as assessed by the investigator according to a 4 point scale: "none", "moderate", "good" or "excellent"), total loss of blood (e.g., intra- and postoperatively, re-bleedings), need of other fibrinogen-containing products (fresh frozen plasma, cryoprecipitate), need of transfusion products (allogenic or autologous blood), and quality of wound healing, whenever applicable. Moreover, the consumption of BT524 required for effective treatment (pre-, intra-, post-operatively) will be calculated. Furthermore, MCF as a surrogate efficacy parameter will be evaluated.

For details regarding the study flowcharts see section 3 of the study protocol.

3.1 Sample size estimation

The primary objectives of this study are key PK parameters. For the PK parameters no formal sample size calculation was carried out. As a general rule approximately 20 patients in this single cohort should suffice to calculate PK parameters with the corresponding range of distribution.

For the surrogate (secondary) efficacy variable MCF, a formal sample size calculation was performed. On the basis of a t-test assessing the difference between dependent means (post minus pre-treatment MCF difference; one sample) the sample size can be calculated. The mean MCF (measured by Fib-tem S of ROTEM) in the study population consisting of patients with congenital fibrinogen deficiency (i.e., a- or severe hypofibrinogenemia) will be determined prior to BT524 treatment and 1 hour after treatment.

With 15 patients, a pre-treatment mean of 4 mm (SD 7 mm) and a post-treatment mean of 10 mm (SD 8 mm) an effect size of 0.8 mm can be detected with a power of 80% at $\alpha = 5\%$ (2-sided) significance level.

3.2 Randomisation, blinding and unblinding procedures

This is an uncontrolled, open-label study design and patients will not be randomized. No special procedures regarding blinding or unblinding are applied.

4 Analysis Sets

4.1 Study populations

4.1.1 Study populations (part I)

Please note, for all part I analysis populations the relevant framework in which to check the criteria (such as informed consent, exposure to BT524, protocol deviation, premature termination etc.) per patient is restricted to the period of its part I participation, i.e. from enrolment in part I up to PK safety visit (Day 49 +/- 4).

PK Set (PK)

The PK population consists of all patients of part I with PK data.

For the PK-specific study population of part I (PK/PD), please see also the PK-Analyses Plan (cf. section 1.1 above).

All Patients Enrolled Set (APE I)

The APE includes all patients who have given informed consent to part I of the study.

Intent to Treat Set (ITT I)

All patients, who received any portion of BT524 in part I of the study.

Full Analysis Set (FAS I)

All patients, who received any portion of BT524 in part I of the study, and have at least one part I efficacy assessment.

Per Protocol Set (PP I)

The PP is a subset of FAS and includes all patients in part I of the study who are compliant with the study protocol without any major protocol deviations in part I thought to have the potential to impact the results of the efficacy analysis (PK/PD).

In the BDRM, dated 25-Jun-2020, all minor and major protocol deviations on patient level were reviewed and agreed upon. Following from the decisions taken, assignments to per-protocol (PP I) analysis population were done. A complete list of all protocol deviations is attached to the meeting minutes of the BDRM, dated 25-Jun-2020, and included in the listings of the final analysis.

Safety Set (SAF I) / Treated Set

The safety population comprises of all patients who were exposed to BT524 in part I of the study.

4.1.2 Study populations (part II)

4.1.2.1 Study populations (part II -patient based)

Please note, for all part II analysis populations the relevant framework in which to check the criteria (such as informed consent, exposure to BT524, protocol deviation, premature termination etc.) per patient is restricted to the period of its part II participation, i.e. from enrolment into solely part II (or for patients who completed Part I from entry in part II defined as 1st day after part I PK safety visit) up to the safety visit (Day 49 +/- 4) of the last treated bleeding event.

All Patients Enrolled Set (APE II)

The APE includes all patients who have given informed consent to exclusive part II of the study and patients consented for Part I/II who completed Part I.

Intent to Treat Set (ITT II)

All patients, who received any portion of BT524 in part II of the study.

Full Analysis Set (FAS II)

All patients, who received any portion of BT524 in part II of the study, and have at least one part II efficacy assessment.

Per Protocol Set (PP II)

The PP is a subset of FAS and includes all patients in part II of the study who are compliant with the study protocol without any major protocol deviations in part II thought to have the potential to impact the results of the efficacy analysis.

In the BDRM, dated 25-Jun-2020, all minor and major protocol deviations on patient level were reviewed and agreed upon. Following from the decisions taken, assignments to per-protocol (PP II) analysis population were done. A complete list of all protocol deviations is attached to the meeting minutes of the BDRM, dated 25-Jun-2020, and included in the listings of the final analysis.

Safety Set (SAF II) / Treated Set

The safety population comprises of all patients who were exposed to BT524 in part II of the study.

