#### • Dosing Day 0 – Pre-dose:

The patient experiencing any bleeding and considered to be eligible for on-demand prophylaxis/on-demand treatment with BT524 for this bleeding event will enter study part II. After having re-checked the inclusion and exclusion criteria, the assessments regarding safety as depicted in the flowchart for *dosing day 0 - pre-dose* have to be performed.

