5.5 Observation and analysis times

Study periods or stages

The study primarily differentiates between the two parts, part I (PK/PD) and part II (ODP/ODT). Within each part different periods are defined:

Part I:

- Screening period: Day -17 to Day -1
- PK/PD assessment/sampling period:
 - Hospitalization from Day 0 (IV infusion) through Day 2
 - Subsequent PK FU from Day 4 through Day 14
- PK safety FU period ending with the PK safety visit at Day 49 (+/- 4)

Accordingly, the participation time for part I is defined as time from screening visit (ICF date) until PK safety visit and defines the analysis time for part I.

Part II periods differ depending on conduct (with or without hospitalization) but are usually ending with the follow up safety visit at Day 49 (+/- 4). Please see the protocol (e.g. section 3) for more details.

Accordingly, the participation time of patients for part II starts

- ⇒ at screening visit (ICF date) for patients solely enrolled in part II or
- ⇒ at 1st day after part I PK safety visit for patients enrolled into part I/II

and lasts until the date of patients study completion/termination.

For the patient based analysis in part II the analysis time is defined by the participation start time until the safety visit (Day 49 +/- 4) of the patients last treated bleeding event.

For the bleeding event based analysis in part II the analysis time of a bleeding event starts with its Treatment Day 0 and ends with its safety visit. Accordingly, data from in-between

individual 49 day periods or after last Day 49 visit will only be listed and not included in the analysis.

For adverse events reporting related periods are defined:

- Patient Enrolment to the First Administration of Study Drug (NTEAE)
- After first Administration of Study Drug until respective Day 49 visit (part I and part II) (TEAE)
- In-between individual 49 day periods or after last Day 49 visit (only related SAEs will be listed and included in the analysis), all other AEs will be counted and listed.

For concomitant medication please refer to section 9.

Study days and bleeding event number

Primarily, study days are counted since first dose of study medication (i.e. in part I) up until the end of study participation.

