11.1 Adverse events

All assessments will be done for all patients, part I and part II separately.

Adverse events (AE) will be coded using the MedDRA® dictionary. The current version will be used at time of database lock and presented by primary System Organ Class (SOC) and Preferred Term.

The analysis will focus on the treatment-emergent AEs (TEAEs). When an AE occurs after written consent has been obtained but before the first dose of study drug, the AE will be considered a non-treatment emergent AE. An AE that occurs (or worsened) on or after the time the patient receives his/her first dose of study drug (until his/her last study visit) will be considered a treatment emergent AE (TEAE). See also CSP section 14.6.2 for definition of non-treatment adverse events.

Please note the definition of study periods and adverse event reporting periods in section 5.5 above. Please also note that analyses for TEAE will be based on the safety population (SAF). Overview tables including non-TEAEs will be based on the APE to also include patients not treated in the study.

For the analysis of TEAEs only those TEAEs are taken into consideration which are reported from first treatment to the safety visit after treatment (independent of the planned duration between treatment start and Day 49 safety visit). For part I this is the duration between PK treatment and the Day 49 PK safety visit or earlier (if a bleeding event happened before Day 49 PK safety visit), and for part II this is for each bleeding event the duration between treatment of the bleeding event and Day 49 safety visit or earlier (if another bleeding event happened before Day 49 safety visit).

All other TEAEs reported out of these time frames will be counted and listed. Exception is the analysis of related serious adverse events (related SAEs) which are included in the analysis irrespective of the onset time after first administration of IMP:

If 'Day 49 safety visit' is not done, the period for inclusion of TEAEs in the analysis is from baseline (treatment start) to 49 days post-baseline.

The total number and percentage of patients reporting at least one AE and the absolute count of AEs will be tabulated for each age group and overall. This initial summary will be based on the APE set and provide a breakdown of the following:

- Any AE
- Any non-severe AE
- Any TEAE
- Any non-serious TEAE
- Any non-severe TEAE
- Any treatment-related TEAE
- Any severe AE

- Any severe TEAE

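### Part II starts on one date for the patient sets and another for adverse events, so a part I patient whose only treated event comes before the PK safety visit falls outside SAF II

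*SAP*

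**What the plan says.** **Sets.** SAP 4.1.2.1 checks every part II set criterion, exposure to BT524 included, only within the patient's part II period. For part I patients that is from "entry in part II defined as 1st day after part I PK safety visit" to the safety visit of the last treated bleed. SAF II requires exposure in part II.

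**Analysis times.** SAP 5.5 starts part II participation "at 1st day after part I PK safety visit for patients enrolled into part I/II", and for patient-based work the "analysis time is defined by the participation start time until the safety visit (Day 49 +/- 4) of the patients last treated bleeding event". Part I time runs "until PK safety visit and defines the analysis time for part I". For event-based work the same section starts the clock at the event's own Treatment Day 0. FBE (SAP 4.1.2.2) takes any treated event with an efficacy assessment and applies no part II start date.

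**TEAE windows.** SAP 11.1 ends the part I window at the PK safety visit "or earlier (if a bleeding event happened before Day 49 PK safety visit"). The part II rule is stated event by event: "for part II this is for each bleeding event the duration between treatment of the bleeding event and Day 49 safety visit", cut short when another bleed comes sooner. "All other TEAEs reported out of these time frames will be counted and listed", except that related SAEs are analysed whenever they begin. TEAE tables use SAF.

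**Protocol.** Protocol 13.1.1.1 foresees a bleed treated before the PK safety visit. It lets that visit be omitted and has the bleed's dosing day 0 and its own Day 49 visit serve instead. Protocol 13.1.2.1 says that a patient with a bleed who is eligible for dosing "with BT524 for this bleeding event will enter study part II". SAP 6.2 dates a missing PK safety visit at 49 days after the PK dose, but only in order to count part I completers.

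**The concern.** The set definitions and the TEAE windows disagree about when part II begins in a situation the protocol expressly allows, and no SAP passage moves the part II start for it. A TEAE can therefore lie in a part II window while its patient is not in the part II safety set. The part I tables do not recover it under 11.1, because the part I window has already closed. SAP 5.5 adds a second conflict: its part I analysis time runs on to the PK safety visit, so under that rule the same TEAE would count in SAF I up to the visit.

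At stake is agreement between FBE and SAF II on who was treated in part II. The SAF II TEAE tables would lose a patient re-exposed within about seven weeks of the PK dose from both numerator and denominator. So would SAF II disposition (14.1.1.2.7), demographics (14.1.2.1.3) and the patient-level antibody table (14.3.4.5.2). Two programmers working from different sections could build different sets.

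**Working it through.** The plan states no figure on this point. The check applies the date rules, then sizes the effect under stated assumptions.

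**1. Date rules.** PK dose = Day 0; one event, one infusion, on Day 20; its safety visit is on Day 20 + 49 = 69. V is the date taken as the PK safety visit. The patient-based part II period is V + 1 to Day 69.

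| Date taken for the PK safety visit | V | Part II period (4.1.2.1, 5.5) | Infusion inside? |
|---|---|---|---|
| Held on Day 49 | 49 | 50 to 69 | No |
| Omitted, dated by SAP 6.2 | 49 | 50 to 69 | No |
| Omitted, bleed's dosing day 0 serves | 20 | 21 to 69 | No |
| Omitted, bleed's own safety visit serves | 69 | 70 to 69 (empty) | No |

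In every row SAP 11.1 gives a part I TEAE window of Days 0 to 20 and a part II window of Days 20 to 69. The patient is outside SAF II each time.

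**2. Boundaries.**
- An event on Day 60 after a visit on Day 49 is in SAF II, as it should be.
- Infusions on Days 20 to 23, with dosing day 0 serving as the visit, put the patient in SAF II: Days 21 to 23 fall after the start. With the visit dated Day 49, the same infusions leave the patient out.
- Infusions on Days 47 to 51 around a Day 49 visit put the patient in SAF II.

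The condition is therefore that all infusions for the only treated event fall on or before the visit date.

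**3. Number of patients.** Planned part I size is 23 (20 aged 6 years or over, 3 younger). The documents give no event rate, so a constant rate r per patient-year is assumed. The chance of at least one treated event within 49 days and none in the following T years is

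f(r, T) = (1 − exp(−49r/365)) × exp(−rT).

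At r = 1 and T = 1: (1 − exp(−0.134)) × exp(−1) = 0.126 × 0.368 = 0.046; times 23 gives 1.06.

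| Expected patients | r = 0.5 | r = 1 | r = 2 | r = 3 | Maximum over r |
|---|---|---|---|---|---|
| All 23 at T = 1 | 0.91 | 1.06 | 0.73 | 0.38 | 1.07 (r = 0.94) |
| 20 at T = 1.75, 3 at T = 1 | 0.66 | 0.58 | 0.24 | 0.08 | 0.67 (r = 0.60) |

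The second row assumes that the first 20 all accept the extension offered in protocol 9 and stay about 21 months (Q2/2018 to Q1/2020). At T = 1.5 for those 20 the maximum is 0.76.

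**4. Missed Day 49 visit (separate and minor).** SAP 11.1 then closes the summary window 49 days after treatment start; protocol follow-up is 49 ± 4 days after the last administration. If infusions span an assumed 3, 7 or 14 days, 49 − 3 = 46, 49 − 7 = 42 or 49 − 14 = 35 days after the last infusion remain in the window.

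**The case against.** The strongest reply is about weight, and most of it stands.

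- **No key analysis is touched.** The primary objective is PK, the one confirmatory test is part I MCF, and the primary part II efficacy analysis is by event. A reader might infer that efficacy loses the event too, because SAP 4.1.2.2 links exclusion from PPBE to exclusion from PP II. The trigger stated there is a major deviation, not a date, so the text does not support that.
- **The data are not lost.** A reader might infer that these TEAEs disappear or that follow-up is cut. Neither is so. The patient is in SAF I through the PK dose, so the pooled SAF I and II tables keep the events. They are listed, can appear in the APE II overview (14.3.1.1.4), and related SAEs are always included.
- **The counts lean high.** PK exclusion criterion 20 bars elective surgery in the 14-day sampling period, and protocol 13.5.1 expects reduced bleeding risk for 1 to 2 weeks after the PK dose. Removing 14 days for all events (35 days at risk) lowers the two maxima from 1.07 to 0.77 and from 0.67 to 0.48. Longer stays lower them further: at an assumed mean of 3 or 4 years for the first 20, the maximum is 0.42 or 0.33 on 49 days.
- **The empty period is one reading only.** A reader might infer that part II always ends before it begins after an early bleed. Protocol 13.1.1.1 names both the bleed's dosing day and its safety visit as the substitute. With the dosing day the period is Days 21 to 69, although the single infusion is still outside it.
- **The case may already be settled.** SAP 6.3 says set assignments were made after the data review meeting of 25 June 2020. The minutes are not among the documents, and the SAP records no rule for this case.

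None of this reconciles 4.1.2.1 and 5.5 with 11.1.

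**Conclusion.** The inconsistency is real: followed as written, the set rule gives the wrong set for an allowed case, whichever date stands for the PK safety visit. It applies when the only treated event is fully infused on or before that date. It does not apply to every part I patient with an early bleed: later treated events, or infusions that run past the start date, bring the patient into SAF II.

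The size is small, probably zero or one patient, on an assumed constant event rate, the planned 23 part I patients and the stays shown. The true number is not in the documents. The effect is confined to the by-part patient-level sets and tables, above all the SAF II TEAE tables. It is worth correcting because one patient is visible in a study of about 36, particularly in the age-group columns. The missed-visit rule is a lesser matter and shortens only a summary window.

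**What to change.** In SAP 4.1.2.1 and 5.5:

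1. For set membership and TEAE attribution, define part II entry for part I patients as the earlier of (a) the day after the PK safety visit and (b) the first BT524 infusion for a bleed or surgery after the PK dose. In the example part II then starts on Day 20, and the sets match the 11.1 windows.
2. State in 5.5 that TEAE attribution follows SAP 11.1.
3. Extend APE II to part I patients who enter by route (b). Otherwise a patient treated on Day 20 who withdraws on Day 30 would be in SAF II but, not having completed part I, outside APE II.
4. State which date ends part I when the PK safety visit is omitted (the Day 0 + 49 rule in SAP 6.2 is one candidate). Assign protocol deviations between the bleed and that date to one part, or explicitly to both.
5. Separately, when a Day 49 visit is missing, count the SAP 11.1 summary window as 49 days from the last infusion for that event.

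If the data review meeting already assigned such a patient, record that rule in the SAP. The cost is a few sentences and small changes to derived dates and set flags, with no new data.
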